### **Analysis of the exploratory PD endpoints**

For biomarkers measured only once post-baseline, a linear fixed-effect model or a rank ANCOVA will be performed similarly to the analyses of the main PD endpoints, on the exploratory PD endpoints (absolute change from baseline and ratio from baseline for markers measured by ICC in BALF and brushing samples, and for different cell counts in BALF; absolute and percent change from baseline for the subepithelial thickness and protein levels; change in gene expression).

For biomarkers measured only twice post-baseline (proteins in blood), a MMRM (or other statistical approaches in case of deviations to the model assumptions) will be performed similarly to the analyses of the additional PD endpoints.

### **Multiplicity issues**

In all statistical models performed, unadjusted (ie, nominal) p-values and p-values adjusted to control the false discovery rate (FDR) using the Benjamini-Hochberg procedure (2) at a 10% threshold will be systematically presented in all outputs.

The adjustment will be done separately for each of group of biomarkers:

- IHC markers in biopsy samples.
- ICC markers in BALF samples.
- ICC markers in brushing samples.
- Subepithelial thickness.
- Differential cell counts in BALF.
- Differential cell counts in blood.
- RNA markers in biopsy.
- RNA markers in BALF.
- RNA markers in brushing.
- Proteins in BALF.
- Proteins in brushing.
- Proteins in blood.
- FeNO.

All the p-values coming from the statistical analyses performed on the corresponding PD endpoints (for absolute change from baseline and ratio from baseline, for all types of markers within a group) will be taken into account for the multiplicity adjustment.

#### **2.6.2.4 Correlation analyses between PD variables at baseline**

Following analyses will be performed using all pooled groups.

Spearman's correlation coefficients and the corresponding nominal p-values will be computed between each pair of biomarkers at baseline and presented graphically using a heatmap. In addition, a correlation network (using Cytoscape© software) will be produced in order to represent the interaction between biomarkers. Scatter plots might be produced for selected parameters

Hierarchical clustering (based on Spearman's dissimilarity and Ward aggregation method) will be also performed for each different set of biomarkers (IHC markers in biopsy sample, ICC markers in BALF, etc.) and overall. A heatmap of each correlation matrix and overall will be represented, and based on the clustering, groups of similar biomarkers may be identified.

In particular, these analyses will enable to understand the correlations of eosinophil counts between the 4 matrices (tissue biopsy, BALF, brushings and blood).

### **2.6.2.5 Correlation analysis between PD variables at baseline and baseline characteristics**

Following analyses will be performed using all pooled groups.

Spearman's correlation coefficients between all PD variables at baseline and quantitative baseline characteristics (demographics, disease characteristics in particular spirometry data) and the corresponding nominal p-values will be computed. Bar charts plots of the biomarker value at baseline according to qualitative baseline characteristics (eg, gender, BMI group) may also be generated.

### **2.6.2.6 Correlation analysis between change from baseline in PD biomarkers and change from baseline in efficacy data at Week 12/EOT**

Following analyses will be performed separately by treatment group using the following efficacy parameters (see [Section 2.7](#) for the definition of parameters):

- Change from baseline in pre-bronchodilator FEV1 and post-BD FEV1 at Week 12/EOT
- Absolute and percent change from baseline in FeNO at Week 12/EOT

Spearman's correlation coefficients and the corresponding nominal p-values will be computed between absolute and percent change from baseline at Week 12/EOT in all biomarkers and change from baseline in efficacy parameter at the same visit. Scatter plots will also be provided for selected PD parameters.

### **2.6.2.7 Specific analyses on eosinophil data**

Following correlation analyses will be performed separately by treatment group, similar to what is described in [Section 2.6.2.6](#):

- Correlations between absolute change from baseline in eosinophils at Week 12/EOT in tissue biopsy, brushing, BALF and blood samples.
- Correlations between percent change from baseline in eosinophils at Week 12/EOT in tissue biopsy, brushing, BALF and blood samples.

In addition, the following descriptive statistics will be provided, by treatment group and by change in blood eosinophils (>0 or ≤0) at W12/EOT:

- N(%) of patients presenting a >0 or ≤0 change from baseline at W12/EOT in eosinophils in biopsy, brushing and BALF samples.
- Descriptive statistics of change from baseline at W12/EOT in eosinophils in biopsy, brushing and BALF samples.

Following correlations with FeNo will be also performed:

- Correlation between absolute change from baseline in eosinophils at Week 12/EOT in vs the absolute change from baseline in FeNO at the same visit, separately for each matrix (blood, biopsy, brushing and BALF).
- Correlation between percent change from baseline in eosinophils at Week 12/EOT in vs the percent change from baseline in FeNO at the same visit, separately for each matrix (blood, biopsy, brushing and BALF).

### **2.6.2.8 Exploratory predictive/prognostic analyses on change from baseline in efficacy data**

#### **Univariate analyses**

For each biomarker, the prognostic and predictive effects of baseline biomarker on change from baseline in efficacy parameters described in [Section 2.6.2.6](#) at Week 12/EOT will be explored, using a linear fixed effect model, with treatment group, region, ICS dose as fixed effects, baseline biomarker and baseline efficacy parameters as continuous covariates, and baseline biomarker-by-treatment group interaction; unadjusted p-values for the baseline biomarker effect (prognostic effect) as well as the for the interaction (predictive effect) will be reported; adjusted p-values for FDR will be also presented (the adjustment will be done for each of type of biomarkers). The biomarkers that will be considered are the main and exploratory PD endpoints.

In case of convergence issues and given the low sample size, some fixed effects (e.g., region, ICS dose) might be removed from the model.

Similar analyses may be performed using binary expression of the biomarker at baseline (high vs low according to LLN or  $<$  vs  $\geq$  median overall groups).

#### **Multivariate analyses**

If some biomarkers show up to be potentially prognostic/predictive in the previous univariate analyses (using change from baseline in efficacy parameters as defined in [Section 2.6.2.6](#)), exploratory multivariate analyses will be performed in order to identify predictive biomarkers and subgroups of patients with enhanced treatment effect. Following analyses may be conducted:

- Linear regressions with baseline levels of several biomarkers as covariates.
- Linear regression with the combination of 2 biomarkers defined as binary criteria as covariate.

A proper cross-validation scheme including the univariate selection step will be put in place to estimate the generalization error of the model.

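### The multivariate step in SAP 2.6.2.8 aims to find predictive biomarkers, but its listed models and its validation target contain no treatment-effect term

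*SAP*

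**What the plan says.** Section 2.6.2.8 has two parts.

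**Univariate analyses.** For each biomarker the model is written out term by term: treatment group, region, ICS dose, the baseline biomarker, the baseline efficacy parameter and the "baseline biomarker-by-treatment group interaction". The main effect is labelled prognostic and the interaction predictive. Unadjusted and FDR-adjusted p-values are reported.

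**Multivariate analyses.** This part is conditional: "If some biomarkers show up to be potentially prognostic/predictive in the previous univariate analyses", then "exploratory multivariate analyses will be performed in order to identify predictive biomarkers and subgroups of patients with enhanced treatment effect". Under the lead-in "Following analyses may be conducted", two models are listed:
- "Linear regressions with baseline levels of several biomarkers as covariates"
- "Linear regression with the combination of 2 biomarkers defined as binary criteria as covariate"

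Validation is described in one sentence: "A proper cross-validation scheme including the univariate selection step will be put in place to estimate the generalization error of the model". No loss function is named, no measure of treatment-effect difference is mentioned, and the rule by which a marker counts as potentially prognostic or predictive is not given.

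**The concern.** A marker is predictive when the treatment effect changes with it. In a linear model that is the biomarker-by-treatment interaction, and the univariate paragraph of the SAP says the same. The two multivariate models as listed have no such term, so they have no parameter that answers the question the step is meant to answer. This is a mismatch between aim and method, beyond brevity.

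Neither the entry condition nor the validation corrects it. Entry is open to prognostic as well as predictive markers. Prediction error for change in FEV1 or FeNO rewards a marker that forecasts outcome in both arms equally, which says nothing about who benefits from dupilumab.

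At stake is the label put on a marker or subgroup at the end of the exercise. Relating baseline characteristics to treatment response is a listed exploratory objective (SAP 1.2.3). With about 42 patients and many markers, a strong prognostic marker could be reported as defining patients with an enhanced dupilumab effect.

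**Working it through.** **1. Sample size.** Section 2.6.2.8 states no figure of its own, so the design figure in section 1.3 fixes N. Inputs there: difference 25 ppb, SD 32 ppb, 21 completers per group, one-sided 5%, stated power 80%. Effect size = 25/32 = 0.78. A two-sample noncentral t calculation gives 80.05% at 21 per group, so the figure reproduces and 21 per arm is used below.

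**2. What each model estimates.** Let the marker's slope on outcome be s0 under placebo and s1 under dupilumab, with equal arms.
- Biomarker-only regression: pooled slope = (s0 + s1)/2.
- Interaction (the SAP's predictive effect): s1 − s0.

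| Marker type | s0 / s1 | Pooled slope | Interaction |
|---|---|---|---|
| Purely prognostic | 0.6 / 0.6 | 0.6 | 0 |
| Symmetric crossover | −0.4 / +0.4 | 0 | 0.8 |
| Active under dupilumab only | 0 / 0.8 | 0.4 | 0.8 |

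The pooled slope does not determine the interaction. A marker with slopes 0 and 0.8 has the same pooled slope as a purely prognostic marker with slope 0.4 in both arms.

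**3. How often each would be flagged.** Assumptions, none of them in the SAP: standardised marker, residual SD 1, the slopes above, two-sided 10% tests, treatment main effect 0 or 0.78. There were 4,000 simulated trials per scenario with 21 per arm.

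| Marker type | Biomarker-only regression | Interaction test |
|---|---|---|
| Purely prognostic | 96–98% | 10% (nominal) |
| Symmetric crossover | 12% | 76–77% |
| Active under dupilumab only | 68–74% | 77% |

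Adding treatment as a main effect alone does not help: the crossover marker is then flagged in 12–13%. The interaction is the missing term.

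**4. Validation target.** In a separate set of 5,000 runs per scenario, a prognostic marker (slope 0.8 in both arms) was placed beside a predictive one (slopes −0.4/+0.4, −0.6/+0.6 or 0/0.8). Leave-one-out squared error for the outcome, with each marker fitted alone, preferred the prognostic marker in 93–99% of runs.

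**The case against.** The strongest reply is that the predictive testing is already done one paragraph earlier. Every main and exploratory biomarker gets an interaction test there, labelled as such and adjusted for FDR. A reader might infer from the multivariate list that a crossover marker would simply be missed, or that the procedure as a whole selects prognostic markers. The SAP does not support either inference, because such a marker is tested and reported before this step begins. That part of the reply stands. It also means the percentages above compare two models; they are not error rates for the full two-step procedure.

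Second, the list is short and also leaves out region, ICS dose and baseline efficacy, so it may be shorthand for extending the univariate model. It is fair that the SAP is silent on interactions and does not exclude them. But the preceding paragraph spells out every term, and someone programming from the list as it stands would leave the interaction out.

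Third, the 12% figure depends on exact symmetry, which makes the pooled slope zero. For a marker active only under dupilumab, little detection is lost. This stands, and it is why the size must be given as a range across marker types.

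Fourth, the generalization error has no stated loss, so reading it as outcome prediction error is the ordinary meaning and not the SAP's explicit choice. The promise to include univariate selection in the cross-validation is a real safeguard against selection bias. It does not change what is being validated, and it needs a stated selection rule to be carried out. A missing rule does not make repetition impossible, since any rule fixed when the scheme is written can be repeated.

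Finally, the step is optional and exploratory in a Phase 2a study. The main endpoints and the FeNO comparison are unaffected.

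**Conclusion.** The point holds in a limited form. Taken as listed, the multivariate models cannot estimate a predictive effect in the SAP's own sense and cannot separate prognostic from predictive markers. An ordinary prediction-error criterion does not repair this.

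The size depends on the marker. A purely prognostic marker is flagged almost always. A symmetric crossover marker is flagged at close to the 10% false-positive rate. A marker active only under dupilumab is flagged nearly as often as by the interaction test, but under a label that cannot be justified. These figures rest on assumed slopes, residual SD 1 and 21 patients per arm; only the 21 per arm comes from the SAP.

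The consequence is confined to how this exploratory step is interpreted. The correction is cheap and makes the method match the stated aim.

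**What to change.** In section 2.6.2.8, Multivariate analyses:
- Write both models with treatment, the biomarkers (or the binary combination), their interactions with treatment, and the covariates of the univariate model (region, ICS dose, baseline efficacy parameter).
- State that a marker or combination is called predictive on the interaction terms only.
- Name the prediction-error loss. Next to it, report the out-of-fold difference in treatment effect between patients predicted to have high and low benefit, with its interval.
- State whichever entry rule is chosen, so that it can be repeated within each fold.

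A hard FDR threshold on the interaction is not needed for this. In 1,500 simulated trials with independent markers and Benjamini-Hochberg at 10%, the −0.4/+0.4 marker passed such a rule in about 47% of runs with a family of 8 markers, and about 30% with 29 (the size of the RNA panel). A rerun gave about 44% and 30%. That is a steep price in a hypothesis-generating step.

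Cost: a few lines of SAP text, modest extra programming, and less precise estimates because terms are added in about 42 patients.

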## **2.7 ANALYSIS OF EFFICACY VARIABLES**

### **2.7.1 Parameters**

All efficacy parameters are exploratory and include:

- Disease-specific efficacy measures: spirometry, asthma control questionnaire 5-question version (ACQ5) score.
- Disease-specific, daily efficacy assessment.

### **2.7.1.1 Disease-specific efficacy measures**

#### **Spirometry**

Spirometry will be done in accordance with meets the 2005 American Thoracic Society (ATS) / European Respiratory Society (ERS) guidelines at screening, Week 2, 4, 6, 8, and 12/EOT, and for patients who do not rollover to the OLE study, Week 14, 18 and 24/EOS. Details about spirometry testing procedure are provided in protocol (section 9.3.1.1).

The exploratory endpoints for spirometry are the following ones:

- Absolute change from baseline in pre-BD FEV1 at Weeks 2, 4, 6, 8 and 12/EOT,
- Percent change from baseline in pre-BD FEV1 at Weeks 2, 4, 6, 8 and 12/ EOT,
- Absolute change from baseline in other lung function measurements (post-BD FEV1, % predicted FEV1, forced vital capacity [FVC], forced expiratory flow [FEF] 25-75%) at Weeks 2, 4, 6, 8 and 12/EOT.

#### **ACQ-5**

The ACQ-5 was designed to measure both the adequacy of asthma control and change in asthma control which occurs either spontaneously or as a result of treatment. The ACQ-5 has 5 questions, reflecting the top-scoring five asthma symptoms: woken at night by symptoms, wake in the mornings with symptoms, limitation of daily activities, shortness of breath and wheeze. Patients are asked to recall how their asthma has been during the previous week and to respond to the symptom questions on a 7-point scale (0=no impairment, 6= maximum impairment; see [Appendix E](#)).

A global score is calculated: the questions are equally weighted and the ACQ-5 score is the mean of the 5 questions and, therefore, between 0 (totally controlled) and 6 (severely uncontrolled). Higher score indicates lower asthma control. Patients with a score below 1.0 reflect adequately controlled asthma and patients with scores above 1.0 reflect inadequately controlled asthma. On the 7-point scale of the ACQ-5, a change or difference in score of 0.5 is the smallest change that can be considered clinically important, corresponding to the Minimal Clinically Important Difference (MCID) defined by the developer.

Based on the manual of ACQ (3), any more than one missing value is not acceptable. If more than one of the questions have missing value, the global score is invalid and will be considered as missing. If only one question has missing score, it will be imputed (pro-rated) using the completed questionnaires from the previous visit. For instance, answer to question 5 is missing at Visit 2, and all questions are completed at Visit 1. Then the question 5 score at Visit 2 is imputed as: (sum of score at Visit 2/sum of scores excluding question 5 at Visit 1) × score of question 5 at Visit 1. If

the questionnaire from the previous visit is not complete either, the missing value will be imputed as the average of the completed questions within the current visit.

The exploratory endpoints for ACQ5 are the following ones:

- Absolute change from baseline in ACQ5 score at Weeks 4, 8, 12/EOT, 16 and EOS.

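### The SAP's rule for one missing ACQ-5 item has no upper bound and no provision for a zero denominator, so a form can be left without a score or receive one above 6 (minor correction)

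*SAP*

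**What the plan says.** All the relevant text is in the ACQ-5 part of SAP Section 2.7.1.1.

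- Items are scored on a "7-point scale (0=no impairment, 6= maximum impairment").
- For the global score, "the ACQ-5 score is the mean of the 5 questions and, therefore, between 0 (totally controlled) and 6 (severely uncontrolled").
- A form with two or more unanswered items has no valid score and counts as missing.
- For a single unanswered item the rule is: "If only one question has missing score, it will be imputed (pro-rated) using the completed questionnaires from the previous visit". The worked illustration, with question 5 missing at Visit 2, is "sum of score at Visit 2/sum of scores excluding question 5 at Visit 1) × score of question 5 at Visit 1".
- There is one fallback: if "the questionnaire from the previous visit is not complete either, the missing value will be imputed as the average of the completed questions" at the current visit.

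The section also gives 0.5 as the minimal clinically important difference (MCID). Change from baseline in the score is an exploratory endpoint.

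**The concern.** A ratio of sums from two visits needs a non-zero denominator, and its product with the previous item needs a ceiling if the result is to stay on the item scale. The SAP supplies neither, yet it says that the score must lie between 0 and 6.

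Two things follow. A patient who answered four of five items may get no score, although the SAP declares a form invalid only when more than one item is missing. Another patient may get a score that the instrument cannot produce. With about 21 patients per group, one gross outlier could visibly move an arm mean on the only asthma-control questionnaire in the plan. The programmer would also have to choose a remedy that the SAP is meant to fix in advance.

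**Working it through.** **Inputs, all from SAP Section 2.7.1.1 except the group size (Section 1.1).** Items run 0 to 6; the score is the mean of five; the MCID is 0.5; there are about 21 patients per group. Let S1 and S2 be the sums of the four other items at the previous and current visits (each 0 to 24), and q the previous value of the missing item (0 to 6). The current-visit sum is read as the sum of the four answered items, the only workable reading.

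**Stated range.** For a complete form the minimum is 5 × 0 / 5 = 0 and the maximum is 5 × 6 / 5 = 6. The SAP's 0 to 6 is reproduced.

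**Formula.** Imputed item = (S2 / S1) × q. Score = (S2 + imputed item) / 5.

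**Zero denominator.** If S1 = 0 the item is undefined. All zeros on those four items is a legitimate, complete answer, so the fallback is not triggered.

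**Out of range.** Three cases, compared with the item capped at 6 and with the SAP's own within-visit mean, S2 / 4:

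| Previous four items; q | Current four items | Imputed item | Score | Score, item capped at 6 | Score, within-visit mean |
|---|---|---|---|---|---|
| 1,1,1,1; 4 | 2,2,2,2 | (8/4) × 4 = 8 | (8+8)/5 = 3.2 | (8+6)/5 = 2.8 | 2.0 |
| 0,0,0,1; 3 | 3,3,3,3 | (12/1) × 3 = 36 | (12+36)/5 = 9.6 | (12+6)/5 = 3.6 | 3.0 |
| S1 = 1; 6 | 6,6,6,6 | (24/1) × 6 = 144 | (24+144)/5 = 33.6 | (24+6)/5 = 6.0 | 6.0 |

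In the first case the item is impossible but the score stays inside 0 to 6, so a range check on the global score alone would miss it.

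**Extent of the arithmetic problem.** There are 25 × 25 × 7 = 4,375 combinations of S2, S1 and q. Of these, 25 × 7 = 175 are undefined. Of the remaining 4,200, 948 give an item above 6 and 469 give a score above 6. These counts describe the formula; they are not probabilities for patients.

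**Effect on an arm mean of 21, for one affected form (simple mean, before model adjustment).**

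- Extreme case: (9.6 − 3.6) / 21 = 6.0 / 21 = 0.29; 0.29 / 0.5 = 57% of the MCID.
- Moderate case: (3.2 − 2.8) / 21 = 0.4 / 21 = 0.02; 0.02 / 0.5 = 4% of the MCID.

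**Whether other text repairs it.** Section 2.11.3 covers reliever inhalations and averages of daily diary data. Section 2.11.5 has no ACQ-5 rule. The statement in Section 2.7.2 that the repeated-measures model uses no imputation is naturally about missing visit scores; read as covering items, it would contradict the scoring rule.

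**The case against.** The strongest reply is that this is an edge case with little at stake. It needs exactly one missing item, and either zeros on the other four at the previous visit or a rise from a low sum. The SAP gives no rate of single missing items. As an assumption only, 42 patients × 3 on-treatment visits (Weeks 4, 8 and 12) is 126 forms; if 1% to 5% lack one item, 1.3 to 6.3 forms use the imputation rules at all, and only some of those would fail. An undefined item costs one visit score, which the model in Section 2.7.2 can accommodate. All efficacy parameters are exploratory, and an item of 36 would be noticed in programming. This stands, and it limits the point to a minor correction. It does not make the rule workable as written, and Section 2.7.2 plans no residual check of the kind given for the main pharmacodynamic endpoints and FeNO.

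The SAP also attributes its missing-item rules to the ACQ manual, which is not at hand; nor is Appendix E. Either may cover these cases. The SAP nevertheless writes out its own formula and fallback, and a reader who follows that text meets both failures.

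Two stronger readings are tempting. A reader might infer that out-of-range values concentrate in responders. They do not: q is at most 6, so the imputed item exceeds 6 only if S2 / S1 exceeds 1, that is, only if the other four items got worse. In the 9.6 example the patient goes from (1 + 3) / 5 = 0.8 to about 3.0 by the within-visit mean. The rule exaggerates a real deterioration. Only the zero denominator is tied to good control at the previous visit. A reader might also count it as an error that an item previously scored 0 is always imputed as 0 when S1 is above 0. That is how pro-rating works; the result is in range, and the correction below leaves it unchanged.

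**Conclusion.** The point holds as a minor correction. Followed literally, the rule gives no score when the other four items were all 0 on a complete previous form. It can give an item as high as 144 and a score as high as 33.6 when those items worsen from a low sum. This contradicts the SAP's own 0 to 6 range.

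For one affected form, the shift in an arm mean of 21 runs from about 0.02 in the moderate example to 0.29 in the extreme one, taking the capped item as the comparison. Using the within-visit mean instead, the extreme case is (9.6 − 3.0) / 21 = 0.31. How often this would happen cannot be estimated from the SAP. No main endpoint and no part of the sample size calculation depends on ACQ-5.

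**What to change.** Keep the formula and add one sentence to the ACQ-5 text in Section 2.7.1.1: *the imputed item is limited to 0-6; if the sum of the other four items at the previous visit is 0, the missing item is imputed as the mean of the four completed items at the current visit.*

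Every form with four answered items then has a score, and the maximum is (24 + 6) / 5 = 6. The second clause only extends the SAP's existing fallback. The cost is that sentence and about two lines of code. The sponsor should first check the cited manual for its own provision and, if the two differ, record the choice before database lock.
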